Medication Adherence. More than 75% of individuals prescribed medications for chronic diseases do not use them as directed and medication non-adherence costs the healthcare system more than \$300 billion annually in preventable hospitalizations.¹⁶ Several factors have been found to be associated with non-adherence including low perceived efficacy of the medication, side effects, complicated medication regimens, poor relationship with the provider, low health literacy, and medication costs and co-pays for prescriptions¹⁷⁻¹⁹. Adherence is particularly low among individuals from disadvantaged communities due to negative perceptions of the healthcare system including less trust in medical providers, lower belief about the efficacy of medication, difficulty accessing services, and lower health literacy²⁰⁻²¹. In fact, developing interventions to improve medication adherence in these populations has been identified as the single best means to reduce health disparities over other targets such as equalizing access to healthcare or reducing provider discrimination²².

Adherence to smoking cessation pharmacotherapies is similarly poor as most people do not use pharmacotherapy when attempting to quit smoking²³, and among individuals who use smoking cessation medication, 69% prematurely quit use of medication²⁴. Rates of non-adherence to NRT are particularly high with approximately 76% prematurely discontinuing NRT²⁴. However, medication adherence is critical for successful cessation and adherence to smoking pharmacotherapies triples the rates of cessation²⁵⁻²⁷. Similar to medication adherence generally, misperceptions about the safety and efficacy of NRT has undermined effective use of these medications, particularly among disadvantaged populations^{24-25; 28-29}. African American smokers report less lifetime use of smoking cessation pharmacotherapy³⁰, hold less positive attitudes about

the use of pharmacotherapy for cessation, report more concerns about the addiction potential, efficacy, potential for interactions with other medications and harms of pharmacotherapy, and are uncertain about the need for pharmacotherapy for cessation relative to White, non-Hispanic smokers³¹⁻³². This mistrust of medications among disadvantaged populations may be a leading factor contributing to racial disparities in smoking cessation and finding novel mechanisms to increase adherence is a critical step to reduce disparities.

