3. A Pilot of In vivo Nicotine Sampling with PQAs. We randomized 47 community corrections smokers to either 4 sessions of In vivo NRT sampling with PQAs between sessions: Session 1 (S1): patch, S2: gum, S3: combination, S4: review quit attempt or 4 sessions of standard smoking cessation counseling (SC) with combination patch and gum. Both interventions were delivered by undergraduate students with minimal training in smoking cessation interventions but who were trained to follow the treatment manual. Medication was provided up to 12 weeks with additional study visits at weeks 8 and 12. In vivo participants demonstrated in session decreases in both withdrawal and craving relative to SC which illustrates the feasibility and acceptability of administering NRT in session to effect. When good adherence was calculated (defined as use of 80% of prescribed doses), participants in the In vivo group had a higher adherence rates to the patch (78.9% vs. 56.3%; $p=0.15$; converted Cohen's $d=0.502$), gum (57.9% vs. 20%; $p=0.026$; converted Cohen's $d=0.828$) and combination NRT (cNRT; 42.1% vs. 20%; $p=0.17$; converted Cohen's $d=0.483$) relative to Controls at Week 4. By Week 8, good adherence to nicotine patch had attenuated, although differences for adherence to gum (54.5% vs. 15.4%; $p=0.04$; converted Cohen's $d=0.91$) and cNRT (36.4% vs. 15.4%, $p=0.237$; converted Cohen's $d=0.498$) remained present between groups. By Week 12, no significant differences on good adherence were noted between the groups. A trend for better short-term abstinence was found for In vivo participants versus SC (10% vs. 0%, $p=0.19$; converted Cohen's $d=0.44$) at Week 4, although these differences attenuated by Week 12. While this study demonstrated good effects of the In vivo construct, this approach has several limitations compared to the proposed approach. First, participants only sampled gum and did not have a choice in the short-acting NRT to use with patch which does not reflect the real-world options for short-acting NRT. In addition, this pilot recruited only participants in community corrections and did not recruit low income participants without criminal justice involvement. While developing effective interventions for criminal justice populations is important, testing this approach with more general populations of low income smokers is needed initially. Finally, this project was a pilot trial with small numbers of participants and did not examine long-term outcomes after the 12 weeks of NRT administration and long-term outcomes are necessary to determine real-world impact.

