To test Aim 3, we will examine medication adherence during the 8 week intervention period between the intervention groups using Chi Square analyses at weeks 6, 9 and 13. Medication adherence will be defined as a self-reported use of taking 80% of medication as prescribed at each time point for both groups (adherent or not adherent). We can also look at adherence as a continuous proportion variable: adherence = number of doses taken / the number of doses given. We will also examine demographic and smoking characteristics (particularly withdrawal, cravings, abstinence self-efficacy, and NRT perceptions) that would be associated with medication adherence at weeks 6, 9 and 13 using logistic regression. These analyses will allow us to examine important associations with medication adherence in these groups.

To examine underlying factors believed to be important for medication adherence, particularly withdrawal, craving, self-efficacy, and perceptions of NRT, we will also examine these factors by intervention groups across time using paired t-tests, as appropriate. We are primarily interested in determining if our In vivo group had decreases in withdrawal and cravings, while increasing abstinence self-efficacy and NRT perceptions relative to the SC group. Given the pilot nature of this intervention, we will be able to examine 24-hour quit attempts and abstinence, but these factors are not the main focus on analyses as we will likely be underpowered to find significant differences on these outcomes with this small of a sample. While 80 participants may seem like a fairly large sample for a pilot study, a sample size between 500-600 participants is typical for most smoking cessation interventions and would be needed to examine important moderators and mediators of cessation. However, we will be able to obtain initial effect sizes that will be useful for determining the appropriate sample size for a fully-scaled R01 project in the future, if this intervention appears promising.

Missing data. There is a high likelihood that we will have participants who may miss an appointment, do not complete the study, or are otherwise lost to follow-up. Because of the potential of bias due to non-missing

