Study Design Considerations. We made several design choices that should be discussed. First, as is appropriate for a pilot trial, issues of feasibility and acceptability are the primary outcomes of interest. In addition, adherence to NRT is the smoking-related primary outcome of interest, rather than cessation. In our sample of participants and using a CO cutoff of 3 ppm, we generally only achieve about a 6-10% abstinence rate at any one time. While this seems low to researchers who are used to using 10 ppm cutoffs, our previous studies do achieve similar abstinence rates when we use the higher cutoff point of 10 ppm as other smoking cessation interventions. We believe that a 10 ppm cutoff is artificially high and classifies light smokers or chippers as abstinent⁷⁰⁻⁷² and we would rather be rigorous in our outcome of cessation. We know from previous studies as well as the existing literature on adherence that approximately half of smokers are adherent to their medications. Given these proportions, we will be able to do better comparisons to determine the underlying factors associated with adherence with a small sample such as 80 participants and would need much larger samples (N=500-600) to examine factors associated with cessation. Further, evidence suggests that adherence to medications is a critical factor in cessation and no interventions have been developed to successfully increase adherence as well as smoking abstinence. This project is the first step in developing an adherence intervention that we believe will also increase cessation. In addition, some may question the rationale for giving the patch with acute NRT product at all sessions and not separating the experience of these products. This design choice was made for two reasons: First, we wanted to normalize the use of combination NRT by setting the expectation from the start that the patch is to be used with short acting NRT. Second, we want smokers to realize that the patch alone may be insufficient to reduce all cravings and withdrawal but that a short acting NRT can be used to relieve these symptoms acutely. Finally, we considered doing a standard NRT education intervention as our control group such as has been tried in the past to examine the impact on adherence and cessation and this would be a good comparator. However, we wanted to pilot this In vivo intervention against what is considered the best practices for smoking cessation as we believe In vivo could potentially be a stand-alone treatment for cessation that would require less therapeutic knowledge and training to implement relative to standard smoking cessation counseling. This is important for dissemination in low-resource settings and for broad dissemination and adoption.

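### The SAP supports N=80 for its adherence-factor models with about half adherent, but its own pilot shows 25–32% on combination NRT; separately, the models need a predictor cap and a small-sample method

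*SAP*

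**What the plan says.** Study Design Considerations (SAP, C. Approach) explains why adherence rather than cessation is the smoking-related primary outcome. It states that earlier studies and the literature show "approximately half of smokers are adherent to their medications". It concludes that these proportions allow better comparisons to "determine the underlying factors associated with adherence with a small sample such as 80 participants", whereas cessation, at 6–10% abstinent, would need 500–600. No alpha, power, effect size or predictor count accompanies this.

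Aim 3 (SAP, Data Management and Statistical Analysis) tests adherence between arms by chi-square at Weeks 6, 9 and 13. It then adds: "We will also examine demographic and smoking characteristics (particularly withdrawal, cravings, abstinence self-efficacy, and NRT perceptions) that would be associated with medication adherence" at the same visits, by logistic regression. It gives no limit on predictors, no selection rule and no small-sample method. Adherence is an 80% threshold, but the SAP does not say whether this applies to the patch, the short-acting product or both.

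The third preliminary study reports the team's own in-session sampling pilot. Good adherence to combination NRT was 42.1% vs 20% at Week 4. At Week 8 the entry reads "cNRT (36.4% vs. 15.4", again in percent. For later follow-up it says only: "By Week 12, no significant differences on good adherence were noted between the groups".

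**The concern.** The sentence supporting 80 participants uses an adherence rate well above what the same team observed for the regimen being tested. Logistic regression draws its information from the smaller outcome group. If a quarter to a third are adherent, that group is a half to two thirds of the size that the SAP implies.

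The modelling plan has a second weakness of its own. Ordinary maximum-likelihood logistic regression with few adherent people per predictor gives log odds ratios that are, on average, too far from zero. The SAP says that pilot data are needed to learn the mechanisms behind adherence, so overstated associations could shape how those mechanisms are understood before a larger trial.

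**Working it through.** **1. Reproduce the pilot figures.** N=80 has no calculation behind it, so there is none to reproduce. The pilot percentages can be checked: recover whole-number counts, apply Pearson chi-square without continuity correction, and compute d = 2φ/√(1−φ²), where φ = √(χ²/n).

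| Outcome | In vivo | SC | Pooled | p | d |
|---|---|---|---|---|---|
| Patch, Week 4 | 15/19 | 9/16 | 24/35 = 69% | 0.150 | 0.502 |
| Gum, Week 4 | 11/19 | 3/15 | 14/34 = 41% | 0.026 | 0.827 |
| Combination, Week 4 | 8/19 | 3/15 | 11/34 = 32% | 0.171 | 0.483 |
| Gum, Week 8 | 6/11 | 2/13 | 8/24 = 33% | 0.043 | 0.909 |
| Combination, Week 8 | 4/11 | 2/13 | 6/24 = 25% | 0.237 | 0.498 |

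All p-values and effect sizes match the SAP to rounding, which supports the recovered counts. The rates are among participants with data: 34–35 of 47 randomised at Week 4 and 24 of 47 at Week 8.

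**2. Expected adherent participants.** Adherent = N × rate. The SAP expects 70–80% retention, and 0.70 × 80 = 56, so take N from 56 to 80.

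| N | at 50% | at 32.4% | at 25% |
|---|---|---|---|
| 80 | 40 | 26 | 20 |
| 56 | 28 | 18 | 14 |

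With arm plus the four named factors (five predictors), there are 14/5 = 2.8 to 26/5 = 5.2 adherent people per predictor on the combination reading.

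**3. Detectable association.** For one predictor, OR per SD = exp[(1.96 + 0.84)/√(N p(1−p))], assuming two-sided 0.05 and 80% power. From 50% to 25% adherent, this moves from 1.87 to 2.06 at N=80 and from 2.11 to 2.37 at N=56.

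**4. Average bias of ordinary logistic regression.** Simulation with assumed inputs: true OR 2 per SD for one predictor, the others null, normal predictors with correlation 0.3. Entries are the average overstatement of the log odds ratio.

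| Predictors | 50% adherent, N=80 to 56 | 25% adherent, N=80 to 56 |
|---|---|---|
| 5 | 10% to 16% | 14% to 21% |
| 10 | 21% to 35% | 28% to 54% |

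One-predictor models are biased by about 5–12%. A repeat with 2,000 data sets per setting moved these figures by no more than about 3 percentage points. On the odds-ratio scale, 14% and 21% turn a true 2.0 into 2^1.14 = 2.20 and 2^1.21 = 2.31.

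**5. Where the bias comes from.** With five predictors, 10 of the 14 points (N=80) and 16 of the 21 (N=56) are already present at 50% adherent; the lower rate adds 4–5 points. With ten predictors it adds 7 points at N=80 and 19 at N=56.

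**6. Firth-penalised fit.** With five predictors and 25% adherent, bias is 0–1% and root mean squared error is 15–25% lower than with the ordinary fit.

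**The case against.** A reader might infer that the optimistic adherence rate is what makes the odds ratios wrong. Step 5 does not support that. Most of the overstatement is there at 50%, so correcting the rate alone would change little.

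A reader might also infer that 80 is shown to be inadequate. The SAP does not claim that 80 is sufficient; it says that adherence allows better comparisons than cessation. At 25–32% adherent against 6–10% abstinent there are still roughly 2.5 to 5 times as many events, so the claim stands.

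Nor is a quarter the established rate. It is the Week 8 figure from 24 people (exact 95% CI 10–47%); Week 4 is 32% (CI 17–51%). It applies only if the 80% rule means the combination. Patch alone was 69% at Week 4, gum was 41%, and the team's bupropion trial gave 44%. The SAP also says: "Rates of non-adherence to NRT are particularly high with approximately 76% prematurely discontinuing NRT". That concerns stopping early, not failing an 80% threshold at a visit, so 24% should not be read from it as an adherence rate.

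The bias is an average tendency. With N=56, 25% adherent and five predictors, about 59% of estimates exceed the true value and 95% interval coverage stays near 95%. The SAP specifies no joint model or predictor count, and it also allows adherence to be analysed as a continuous proportion.

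All of this stands, and it limits the point to secondary analyses. It does not answer the missing product definition, the missing predictor limit, or the availability of a method with less bias and less error.

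**Conclusion.** Two separate points hold. First, the stated rate of about half conflicts with the SAP's own combination-NRT data (25–32%). On that reading the models would have about 14–26 adherent participants instead of 28–40. This depends on which product the 80% rule covers, and on a small pilot with substantial missing data and no Week 12 percentages.

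Second, ordinary logistic regression in 56–80 people with an unrestricted predictor list overstates associations on average. With five predictors the overstatement of the log odds ratio is 10–16% at 50% adherent and 14–21% at 25%; it is larger with ten and modest with one. The size rests on the assumed odds ratio of 2, the predictor counts and the correlation of 0.3, none of which the SAP gives. The main causes are small N and the open list.

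A reader might extend this to the arm comparison of adherence. The documents do not support that, because those tests are chi-square and involve no predictors. This is a worthwhile improvement to a secondary analysis.

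**What to change.** - In Study Design Considerations, beside the statement of about half, give the pilot combination-NRT range (25–32%) and the expected number of adherent participants (about 14–26 for 56–80 evaluable).
- In Aim 3, state whether the 80% rule covers the patch, the short-acting product or both.
- In Aim 3, limit the joint model at each visit to arm plus withdrawal, craving, abstinence self-efficacy and NRT perceptions, with one prespecified score for each, and fit it by Firth-penalised logistic regression.
- Report every other characteristic one at a time as an odds ratio with a 95% CI, labelled descriptive.

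The cost is SAP wording and access to a penalised-regression routine; the SAP names SPSS and does not say whether one is available. No extra recruitment or data collection is needed. The downsides are fewer predictors in the joint model and a less favourable stated adherence rate.
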